7.7 Concomitant Medication

To the extent possible, administration of any prescription or over-the-counter drug products other than study medication should be minimised during the study period. Subjects should be discouraged from use of herbal remedies, tobacco products, or excessive alcohol at any time during the clinical study.

If considered necessary for the subject's well-being, drugs for concomitant medical conditions or for symptom management may be given at the discretion of the investigator.

Subjects should be instructed about the importance of the need to inform the clinic staff of the use of any drugs or remedies (whether prescribed, over-the-counter, or illicit) before and during the course of the study. Any concomitant drugs taken by a subject during the course of the study and for 30 days post the last dose of study treatment should be recorded in the medical record and the CRF with the reason for use.

REFER TO APPENDIX 10 FOR A LIST OF CAUTIONED AND PROHIBITED MEDICATION.

7.7.1 Prohibited concomitant medications

- Warfarin
- Any chemotherapy, anticancer immunotherapy, corticosteroids (at doses equivalent to prednisone >20 mg per day), experimental therapy, or radiotherapy are prohibited while the patient is receiving ibrutinib treatment.
- Vaccination with live vaccines
- Both ibrutinib and obinutuzumab are contraindicated in patients with clinically significant hypersensitivity to the compound itself or to its excipients
- ACE inhibitors and ARBs

The Sponsor must be notified in advance (or as soon as possible thereafter) of any instances for which prohibited therapies are administered.

Please consult with the CI and Clinical Coordinators via the trials office if unsure about the use of a specific drug.

7.7.2 Concomitant Medications to be Used With Caution with ibrutinib

Agents that may increase ibrutinib plasma concentrations:

Ibrutinib is metabolized primarily by CYP3A. Avoid co-administration with strong CYP3A4 or moderate CYP3A inhibitors and consider alternative agents with less CYP3A inhibition.

If a strong CYP3A inhibitor (eg, ketoconazole, indinavir, nelfinavir, ritonavir, saquinavir, clarithromycin, telithromycin, itraconazole, nefazadone, or cobicistat) must be used, reduce ibrutinib dose to 140 mg for the duration of the inhibitor use or withhold treatment temporarily (for 7 days or less).. Subjects should be monitored for signs of ibrutinib toxicity.

If a moderate CYP3A inhibitor (eg, voriconazole, erythromycin, amprenavir, aprepitant, atazanavir, ciprofloxacin, crizotinib, darunavir/ritonavir, diltiazem, fluconazole, fosamprenavir, imatinib, verapamil, amiodarone, or dronedarone) must be used, reduce ibrutinib to 280 mg for the duration of the inhibitor use. Avoid grapefruit and Seville oranges during ibrutinib/placebo treatment, as these contain moderate inhibitors of CYP3A

No dose adjustment is required in combination with mild inhibitors.

Avoid concomitant use of strong CYP3A inducers (eg, carbamazepine, rifampin, phenytoin, and St. John's Wort). Consider alternative agents with less CYP3A induction.

A list of common CYP3A inhibitors and inducers is provided in Appendix 10. A comprehensive list of inhibitors, inducers, and substrates may be found at <http://medicine.iupui.edu/clinpharm/ddis/main-table/>. This website is continually revised and should be checked frequently for updates.

For the most comprehensive effect of CYP3A inhibitors or inducers on ibrutinib exposure, please refer to the current version of the IB.

Agents that may decrease ibrutinib plasma concentrations:

Administration of ibrutinib with inducers of CYP3A4 can decrease ibrutinib plasma concentrations.

Co-administration of ibrutinib with strong CYP3A inducers, rifampin, in healthy subjects decrease ibrutinib plasma concentrations by approximately 10-fold. Avoid concomitant use of strong CYP3A inducers (eg, carbamazepine, rifampin, phenytoin, and St. John's Wort). Consider alternative agents with less CYP3A induction.

If the benefit outweighs the risk and a strong or moderate CYP3A4 inducer must be used, monitor patient closely for lack of efficacy (see sections 4.3 and 4.4). Mild inducers may be used concomitantly with ibrutinib. However, patients should be monitored for potential lack of efficacy. As ibrutinib solubility is pH dependent, there is a theoretical risk that medicinal products increasing stomach pH (e.g. proton pump inhibitors) may decrease ibrutinib exposure.

A list of common CYP3A inhibitors or inducers is provided in Appendix 10.

Drugs That May Have Their Plasma Concentrations Altered by ibrutinib

In vitro studies carried out by Pharmacyclics indicated that ibrutinib is a weak inhibitor toward CYP2B6, CYP2C8, CYP2C9, CYP2C19, CYP2D6, and CYP3A4/5 and does not display time-dependent CYP450 inhibition. The dihydrodiol metabolite of ibrutinib is a weak inhibitor toward CYP2B6, CYP2C8, CYP2C9, and CYP2D6. Both ibrutinib and the dihydrodiol metabolite are at most weak inducers of CYP450 isoenzymes *in vitro*. Therefore, it is unlikely that ibrutinib has any clinically relevant drug-drug interactions with drugs that may be metabolized by the CYP450 enzymes.

In vitro studies indicated that ibrutinib is not a substrate of P-gp, but is a mild inhibitor. Ibrutinib is not expected to have systemic drug-drug interactions with P-gp substrates. However, it cannot be excluded that ibrutinib could inhibit intestinal P-gp after a therapeutic dose. There are no clinical data available, therefore co-administration of narrow therapeutic index P-gp substrates (e.g., digoxin) with ibrutinib may increase their blood concentration and should be used with caution. Patients monitored closely for toxicity.

QT Prolonging agents

Any medications known to cause QT prolongation should be used with caution; periodic monitoring with ECGs and electrolytes should be considered and if needed, a medical monitor may be contacted.

Prohibited Concomitant Medications

Any chemotherapy, anticancer immunotherapy, corticosteroids (at doses equivalent to prednisone >20 mg per day), experimental therapy, or radiotherapy are prohibited while the subject is receiving ibrutinib treatment. Short courses (<14 days) of treatment for non-cancer-related medical reasons (treatment for autoimmune cytopenias are permitted) at doses that do not exceed 100 mg per day of prednisone or equivalent are permitted.

Warfarin or vitamin K antagonists should not be administered concomitantly with ibrutinib.

Erythropoietic growth factors (eg, erythropoietin), platelet growth factors (eg, thrombopoietin), and sargamostim are also prohibited.

The Sponsor must be notified in advance (or as soon as possible thereafter) of any instances which prohibited therapies are administered.

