	Second	Withhold until recovery to \leq Grade 1 or baseline; may restart at 1 dose level lower (280 mg per day)
	Third	Withhold until recovery to \leq Grade 1 or baseline; may restart at 1 dose level lower (140 mg per day)
	Fourth	Discontinue

At the Investigator's discretion, the dose of ibrutinib may be re-escalated after 2 cycles of a dose reduction in the absence of a recurrence of the toxicity that led to the reduction.

Dose Modification for Hepatic Impaired Subjects

Ibrutinib is metabolized in the liver and therefore subjects with clinically significant hepatic impairment at the time of screening (Child- Pugh class B or C) are excluded from study participation.. Concomitant use of strong CYP inhibitors is not permitted in subjects with chronic hepatic impairment. For subjects with existing chronic mild hepatic impairment (Child-Pugh class A) at enrolment, the starting dose has to be adjusted to a level of 280 mg daily (two capsules). For subjects who develop mild liver impairment while on study (Child-Pugh class A), the recommended dose reduction for ibrutinib is to a level of 280 mg daily (two capsules). For subjects who develop moderate liver impairment while on study (Child-Pugh class B), the recommended dose reduction is to a level of 140 mg daily (one capsule). Subjects who develop severe hepatic impairment (Child-Pugh class C) must hold study drug until resolved to moderate impairment (Child-Pugh class B) or better. Subjects who develop acute hepatic toxicity with liver enzymes Grade 3 or higher while on study should be managed per standard dose modification guidelines in Section 7.4.

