APPENDIX 10 – CAUTIONED AND PROHIBITED MEDICATION

Some inhibitors of CYP3A4/5 are defined below.

Some cautioned and prohibited medications are listed below. This list is not exhaustive, any new medications should be reviewed with guidance from pharmacy in order to identify potential interactions.

Class of drug	Examples	During trial
Strong inhibitors of CYP3A	Boceprevir, clarithromycin, cobicistat, conivaptan, itraconazole, ketoconazole, nefazodone, nelfinavir, posaconazole, ritonavir (alone or in combination with one or more of the following: danoprevir, elvitegravir, indinavir, lopinavir, ombitasvir, paritaprevir, saquinavir, tipranavir), telaprevir, telithromycin, troleandomycin, voriconazole. Grapefruit juice, Seville oranges, starfruit.	Avoid the use of these drugs If a strong CYP3A inhibitor must be used, reduce ibrutinib dose to 140 mg or withhold treatment for the duration of inhibitor use withhold treatment temporarily (for 7 days or less). Patients should be monitored for signs of ibrutinib toxicity. If the patient must receive these drugs the patient must be monitored for toxicity.
Moderate inhibitors of CYP3A	Aprepitant, cimetidine, ciprofloxacin, clotrimazole, crizotinib, cyclosporine, dronedarone, erythromycin, fluconazole, fluvoxamine, imatinib, tofisopam, verapamil.	Avoid the use of these drugs If a moderate CYP3A inhibitor must be used, reduce ibrutinib dose to 280 mg or withhold treatment for the duration of inhibitor use. Patients should be monitored for signs of ibrutinib toxicity. If the patient must receive these drugs the patient must be monitored for toxicity.
Weak inhibitors of CYP3A	Chlorzoxazone, cilostazol, fosaprepitant, istradefylline, ivacaftor, lomitapide, ranitidine, ranolazine, tacrolimus, ticagrelor.	These drugs may be administered and patients should be monitored for any toxicity/lack of efficacy.
Strong inducers of CYP3A	Carbamazepine, enzalutamide, mitotane, phenytoin, rifampicin, St. John's wort.	Avoid the use of these drugs. Where use cannot be avoided this should be discussed with the Chief Investigator/Clinical Coordinator via the Trial Office. If the patient must receive these drugs the patient must be monitored for lack of efficacy.

Class of drug	Examples	During trial

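### Voriconazole is a moderate CYP3A inhibitor in section 7.7.2 (ibrutinib 280 mg) but a strong one in Appendix 10 (140 mg or withhold), and the strong-inhibitor exclusion cites the wrong section

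*Protocol*

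**What the plan says.** Protocol section 7.7.2 advises against combining ibrutinib with strong or moderate CYP3A inhibitors, then says what to do when one is unavoidable. Its moderate list begins "If a moderate CYP3A inhibitor (eg, voriconazole, erythromycin, amprenavir, aprepitant, atazanavir, ciprofloxacin", and the instruction for that class is to "reduce ibrutinib to 280 mg for the duration of the inhibitor use". Its strong list has ten examples, and voriconazole is not among them. For strong inhibitors the instruction is 140 mg while the inhibitor is used, or withholding for up to 7 days. The section adds: "Avoid grapefruit and Seville oranges during ibrutinib/placebo treatment, as these contain moderate inhibitors of CYP3A". It then points onward: "A list of common CYP3A inhibitors and inducers is provided in Appendix 10". Sections 7.1.1 and 7.7 also send the reader to Appendix 10.

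Appendix 10 ends its strong row with "telaprevir, telithromycin, troleandomycin, voriconazole. Grapefruit juice, Seville oranges, starfruit" and instructs: "If a strong CYP3A inhibitor must be used, reduce ibrutinib dose to 140 mg or withhold treatment". Voriconazole does not appear in its moderate row.

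Two other rules depend on the class. Section 4.2 and the Trial Synopsis exclude patients who need a strong CYP3A4/5 inhibitor, and both refer to section 7.8.2. Section 7.4.1 states: "Concomitant use of strong CYP inhibitors is not permitted in subjects with chronic hepatic impairment".

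**The concern.** One named drug carries two classes and two ibrutinib doses in the same version of the protocol. A reader who stops at 7.7.2 finds a complete instruction for voriconazole by name and has no reason to look further. A reader who goes to Appendix 10 finds a different one.

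Three decisions follow from the class: the ibrutinib dose during voriconazole, whether a patient needing voriconazole at entry is excluded, and whether voriconazole may be given at all to a patient with chronic hepatic impairment. The situation is foreseeable. Section 7.8.12 reports fungal infections on ibrutinib, and 7.9.4 advises considering antifungal prophylaxis in severe, prolonged neutropenia, although neither names an agent. Ibrutinib continues until progression or the MRD stopping rules apply, so the instruction matters for anyone still on treatment, whether or not recruitment is open.

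**Working it through.** The protocol states no statistical figure on this point, so the check compares the texts and adds simple arithmetic.

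**Voriconazole, side by side**

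| | Section 7.7.2 | Appendix 10 |
|---|---|---|
| Class | Moderate | Strong |
| First advice | Avoid | Avoid |
| If it must be used | 280 mg | 140 mg or withhold |
| Share of 420 mg | 280/420 = 67% | 140/420 = 33%, or 0 if withheld |

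The ratio of the two reduced doses is 280/140 = 2.0. This compares prescribed doses, not drug exposure or harm.

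**Chronic hepatic impairment (7.4.1).** A Child-Pugh A patient starts at 280 mg. If voriconazole is moderate, the 7.7.2 instruction changes the dose by 280 − 280 = 0 mg. If it is strong, the combination is not permitted.

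**How far the mismatch extends.** Section 7.7.2 calls 17 items moderate: 15 drugs plus grapefruit and Seville oranges. Against Appendix 10:

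- 8 agree: erythromycin, aprepitant, ciprofloxacin, crizotinib, fluconazole, imatinib, verapamil, dronedarone.
- 3 are strong there: voriconazole, grapefruit (as juice), Seville oranges.
- 1 is arguable: darunavir/ritonavir. Appendix 10's strong row has "ritonavir (alone or in combination with one or more of the following: danoprevir, elvitegravir, indinavir" and further partners, but darunavir is not named.
- 5 are not listed: amprenavir, atazanavir, diltiazem, fosamprenavir, amiodarone. The appendix says its list is not exhaustive, so these are not conflicts.

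8 + 3 + 1 + 5 = 17. In the other direction, none of the ten strong examples in 7.7.2 is moderate in Appendix 10: eight are listed there in their own right, and two (indinavir, saquinavir) only as ritonavir combinations. Grapefruit and Seville oranges have little consequence, since both places say to avoid them. Voriconazole is the one drug with a clear dose consequence.

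**The withholding wording.** Section 7.7.2 limits withholding with a strong inhibitor to 7 days or less. The strong row of Appendix 10 runs together withholding for as long as the inhibitor is used and the 7-day limit. Moving voriconazole to the strong list in 7.7.2 would therefore not by itself give one instruction.

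**The cross-reference.** Section 7.8.2 covers overdose and contains nothing on CYP3A. The inhibitor guidance is in 7.7.2 and Appendix 10.

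**The case against.** The best case for leaving this alone is that several safeguards stand between the text and a wrong dose. Both places say to avoid the drug, and three sections route the reader to Appendix 10, the more cautious text. Appendix 10 calls for pharmacy guidance on new medications and for toxicity monitoring. Section 7.7.2 also refers to an external inhibitor list and the current Investigator Brochure, and 7.7.1 tells sites to consult if unsure. These lower the risk, but none says which text prevails, and someone who has read only one place has no cause to be unsure.

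Four narrower points have force:

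- The absence of a further reduction in Child-Pugh A applies to every moderate inhibitor, so reclassifying voriconazole would not close that gap for the others. The bar on strong inhibitors does turn on the class.
- Appendix 10 also allows withholding with moderate inhibitors, so withholding does not separate the classes within the appendix. The contrast above is between the two instructions a site would read for voriconazole, and the core of it is 280 versus 140 mg.
- The wrong cross-reference is editorial, and a correct pointer to 7.7.2 would not settle the class until the lists agree.
- The eligibility effect is narrow, because active infection and a history of chronic or recurrent infection are already exclusions.

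**Conclusion.** The concern holds. The current protocol gives two incompatible instructions for ibrutinib with voriconazole, differing twofold in prescribed dose (280 versus 140 mg) where ibrutinib is not withheld. The same ambiguity carries into the strong-inhibitor exclusion and the hepatic-impairment rule. This is an internal inconsistency in a dosing rule and should be fixed. It does not touch the primary endpoint, the activity decision rule or the stopping rules.

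The conclusion rests only on the text of the two lists. It does not need a judgement on which class is pharmacologically right, and the protocol cannot supply one. How often the conflict would arise is unknown, because the protocol gives no figure for voriconazole use. Grapefruit, Seville oranges, darunavir/ritonavir and the cross-reference are minor additions.

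**What to change.** - Give voriconazole one class and one instruction. By default adopt the Appendix 10 class and move it to the strong list in 7.7.2, unless the clinical team decides otherwise from the current Investigator Brochure.
- Put the 7.7.2 strong-inhibitor instruction into the strong row of Appendix 10: 140 mg while the inhibitor is used, or withhold for no more than 7 days.
- Align grapefruit and Seville oranges between the two places, and check the class of darunavir/ritonavir.
- In section 4.2 and the Trial Synopsis, replace the reference to 7.8.2 with 7.7.2 and Appendix 10.
- Notify sites that have patients on ibrutinib.

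The cost is one clarifying amendment and one site memo. No procedures, visits or patients are added.

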7.7.3 Concomitant Medications and Obinutuzumab

No formal drug-drug interaction studies have been performed, although limited drug interaction studies have been undertaken for obinutuzumab with bendamustine, CHOP (cyclophosphamide,

doxorubicin, vincristine, prednisolone), and FC (fludarabine, cyclophosphamide) and chlorambucil. Co-administration with obinutuzumab had no effect on the pharmacokinetics of bendamustine, FC, chlorambucil or the individual components of CHOP; in addition, there were no apparent effects of bendamustine, FC, chlorambucil or CHOP on the pharmacokinetics of obinutuzumab. A risk for interactions with concomitantly used medicinal products cannot be excluded.

Immunisation with live or attenuated viral vaccines, following obinutuzumab treatment has also not been studied, therefore the vaccination with live vaccines is not recommended during treatment and until B-cell recovery.

7.8 Precautions for ibrutinib use

7.8.1 Antiplatelet Agents, Anticoagulants and Bleeding Related Events

Warfarin or vitamin K antagonists should not be administered concomitantly with ibrutinib. Supplements such as fish oil and vitamin E preparations should be avoided during treatment with ibrutinib. Use ibrutinib with caution in subjects requiring other anticoagulants or medications that inhibit platelet function. Subjects with congenital bleeding diathesis have not been studied. Subjects requiring the initiation of therapeutic anticoagulation therapy (e.g., atrial fibrillation),.. If therapeutic anticoagulation is clinically indicated, treatment with ibrutinib should be held and not be restarted until the subject is clinically stable and has no signs of bleeding. Subjects should be observed closely for signs and symptoms of bleeding. No dose reduction is required when study drug is restarted.

Patients participating in IcICLLe will be monitored closely for haemorrhagic adverse events. Ibrutinib should be held at least 3 to 7 days pre and post-surgery depending upon the type of surgery and the risk of bleeding (see section 7.8.3).

7.8.2 Overdose

Any dose of study drug in excess of that specified in this protocol is considered to be an overdose. Signs and symptoms of an overdose that meet any Serious Adverse Event criterion must be reported as a Serious Adverse Event in the appropriate time frame and documented as clinical sequelae to an overdose.

There is no specific experience in the management of ibrutinib overdose in patients. No maximum tolerated dose (MTD) was reached in the Phase 1 study in which subjects received up to 12.5 mg/kg/day (1400 mg/day). Healthy subjects were exposed up to single dose of 1680 mg. One healthy subject experienced reversible Grade 4 hepatic enzyme increases (AST and ALT) after a dose of 1680 mg. Subjects who ingested more than the recommended dosage should be closely monitored and given appropriate supportive treatment.

7.8.3 Guidelines for ibrutinib management with surgeries or procedures

Ibrutinib may increase the risk of bleeding with invasive procedures or surgery. The following guidance should be applied to the use of ibrutinib in the perioperative period for subjects who require surgical intervention or an invasive procedure while on study.

- For any surgery or invasive procedure requiring sutures or staples for closure, ibrutinib should be held at least 7 days prior to the intervention and should be held at least 7 days after the procedure and restarted at the discretion of the investigator when the surgical site is reasonably healed without serosanguineous drainage or the need for drainage tubes.
- For minor procedures (i.e. such as a central line placement, needle biopsy, thoracentesis, or paracentesis) ibrutinib should be held for at least 3 days prior to the procedure and should not be restarted for at least 3 days after the procedure. For bone marrow biopsies that are performed while the subject is on ibrutinib, it is not necessary to hold ibrutinib for these procedures.
- For emergency procedures, ibrutinib should be held after the procedure until the surgical site is reasonably healed, for at least 7 days after the urgent surgical procedure.

7.8.4 Treatment related lymphocytosis

Similar to other agents targeting B-cell receptor signalling, transient lymphocytosis is a pharmacodynamic effect of ibrutinib, in which the inhibition of BTK-mediated cellular homing and adhesion results in a mobilization of tumour cells to the peripheral blood (Stevenson 2011).

Upon initiation of treatment, a transient phase of increase in lymphocyte counts (i.e., $\geq 50\%$ increase from baseline and above absolute count 5000/mcL), often associated with reduction of lymphadenopathy, has been observed in most patients (75%) with relapsed/refractory CLL/SLL treated with ibrutinib. This effect has also been observed in some patients (33%) with relapsed/refractory MCL treated with ibrutinib. This observed transient lymphocytosis is usually not associated with an adverse event and should not be considered progressive disease in the absence of other clinical findings. In both disease types, lymphocytosis typically occurs during the first few weeks of ibrutinib therapy (median time 1.1 weeks) and resolves within a median of 18.7 weeks in CLL patients. A large increase in the number of circulating lymphocytes (eg, $>400,000/\text{mcL}$) has been observed in some subjects.

